## 8.3 Hypotheses/Estimation

Objectives and hypotheses of the study are stated in Section 3.0.

## 8.4 Analysis Endpoints

Efficacy and safety endpoints are listed below, followed by the descriptions of the derivations of selected endpoints.

### 8.4.1 Efficacy/Immunogenicity/Pharmacokinetics Endpoints

Efficacy endpoints and their definitions are presented in Section 8.4.3.

### 8.4.2 Safety Endpoints

The primary safety endpoint is DLT. Safety will be monitored by cumulative data reviews throughout the trial. The toxicities and grades experienced by subjects who have received study treatment, including adverse events (AEs), serious adverse events (SAEs) and events of clinical interest (ECIs) will be summarized. Other safety measures evaluated in all parts of the study include laboratory safety assessments, ECGs, vital signs, and physical examinations.

### 8.4.3 Derivations of Efficacy/Immunogenicity/Pharmacokinetics Endpoints

Exploratory efficacy endpoints and their definitions are presented below.

**Objective Response Rate (ORR):** is defined as the percentage of subjects who have achieved confirmed complete response (CR) or partial response (PR) according to irRECIST by the investigator review. Subjects with missing outcome on objective response will be considered non-responders.

**Disease Control Rate (DCR):** is defined as the percentage of subjects who have achieved stable disease for at least 8 weeks or confirmed complete response (CR) or confirmed partial response (PR) according to irRECIST by the investigator review. Subjects with missing response will be considered not to have achieved DCR.

**Duration of Response (DOR):** is defined as the time interval between the date of the first confirmed response (CR/PR) (the response prior to confirmation) and the date of first documented disease progression based upon irRECIST by the investigator review. Response duration will be only determined for confirmed responses.

**Best Overall Response** per irRECIST [Appendix 12.6]: the best response attained during the study with 4 categories based upon irRECIST by the investigator review: Complete Response (CR), Partial Response (PR), Stable Disease (SD), and Progressive Disease (PD). Categories of CR and PR need to be confirmed in this endpoint.

**Progression-free Survival (PFS)**: is defined as the time from the start of treatment to progressive disease (PD) or death, whichever occurs earlier, based upon irRECIST by the investigator review. Subjects without documented PD/death will be censored at the last disease assessment date.

**Best Target Lesion Response** - maximum percent reduction in tumor line length over target lesions by the investigator review.

**Time to Confirmed Response** - defined only for subjects with confirmed response by the investigator review - the time interval between the start of treatment allocation and the date of the first confirmed response (CR/PR) (the response prior to confirmation).

Additional supportive analyses of these endpoints based on RECIST criteria and, if needed, central review might be conducted.

**PK endpoints**- serum concentrations of MK-1248 and pembrolizumab and derived PK parameters.

**Target engagement endpoints** – to be used in descriptive analyses

**Biomarker endpoints**– to be used in descriptive analyses

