## 1.0 TRIAL SUMMARY

Abbreviated Title	Phase 1 Trial of MK-1248 as Monotherapy and in Combination with Pembrolizumab in Subjects with Advanced Solid Tumors
Trial Phase	Phase 1
Clinical Indication	Treatment of subjects with advanced solid tumors
Trial Type	Interventional
Type of control	None
Route of administration	Intravenous
Trial Blinding	Unblinded Open-label
Treatment Groups	Subjects will be allocated by non-random assignment to one of 2 treatment arms: Arm 1: MK-1248 as monotherapy Arm 2: MK-1248 in combination with pembrolizumab
Number of trial subjects	Approximately 96 subjects will be enrolled.
Estimated duration of trial	The sponsor estimates that the trial will require approximately 4 years from the time the first subject signs the informed consent until the last subject's last visit.
Duration of Participation	Each subject will participate in the trial from the time the subject signs the Informed Consent Form (ICF) through the final contact. After a screening phase of up to 28 days, each subject will be allocated by non-random assignment into one of two arms and receive treatment with MK-1248 alone or in combination with pembrolizumab. Study treatment in both arms will begin on Day 1 of each 3-week cycle. For subjects enrolled in Arm 1 and Arm 2, treatment with MK-1248 will end after 4 cycles; treatment with pembrolizumab in Arm 2 will continue for up to 24 months. Treatment in both arms will continue until disease progression, unacceptable adverse event(s), intercurrent illness that prevents further administration of treatment, Investigators decision to withdraw treatment, subject withdraws consent, pregnancy of the subject, noncompliance with study treatment or procedure requirements, subject completes treatment, or administrative reasons requiring cessation of treatment. After the end of treatment, each subject will be followed for 30 days for adverse event monitoring (serious adverse events will be collected for 90 days after the end of treatment, or 30 days after the end of treatment if the subject initiates new anticancer therapy, whichever is earlier).

Enrollment into this study has been prematurely discontinued due to program prioritization and not related to any safety concerns. The cut-off date for enrollment is 31-Mar-2017.

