#### **5.2.1.5 Dose Confirmation**

The objective of dose confirmation in Part C and Part E is to refine the estimate of the MK-1248 MTD based on TPI design [1] with target toxicity rate  $\leq 30\%$ . Dose confirmation involves the expansion of at least 1 dose level studied in the dose escalation stage of the study.

The toxicity probability interval (TPI) design [1] will be used at the dose confirmation stage. Based on the observed DLTs, the approach recommends actions of escalating, staying at, or de-escalating the dose level as presented in [Table 4](#).

Dose confirmation will begin with expansion of the preliminary MTD/MAD identified in the dose escalation stage described above. The dose confirmation part will continue until 14 subjects are studied at the selected dose (combined from dose escalation and dose confirmation) with  $\leq 5$  of 14 subjects experiencing a DLT. As subjects become evaluable for DLT assessment, the number of subjects who are evaluable for DLT versus the number of subjects who developed a DLT will be continuously assessed and de-escalation and re-escalation to eligible doses of MK-1248 will occur as shown in [Table 4](#)

The 200 mg dose of pembrolizumab will not be adjusted.

Table 4 Dose Confirmation Rules

Number of toxicities	Number of subjects treated at current dose										
	4	5	6	7	8	9	10	11	12	13	14
0	S	E	E	E	E	E	E	E	E	E	E
1	S	S	S	S	S	S	E	E	E	E	E
2	D	S	S	S	S	S	S	S	S	S	S
3	DU	D	D	S	S	S	S	S	S	S	S
4	DU	DU	DU	D	D	D	S	S	S	S	S
5		DU	DU	DU	DU	DU	D	D	S	S	S
6			DU	DU	DU	DU	DU	DU	D	D	D
7				DU	D						
8					DU						
9						DU	DU	DU	DU	DU	DU
10							DU	DU	DU	DU	DU
11								DU	DU	DU	DU
12									DU	DU	DU
13										DU	DU
14											DU

E = Escalate to the next higher dose  
 S = Stay at the current dose  
 D = De-escalate to the next lower dose  
 DU = The current dose is unacceptably toxic  
 Target toxicity rate = 30%  
 a=1; b=1; k1=1; k2=1.5; pow=1 per [1].

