### **8.5.2 Efficacy Analysis Populations**

The full analysis set populations FAS1 and FAS2 are defined as all subjects with a baseline scan with measurable disease by investigator assessment who were administered MK-1248 (Arm 1; FAS1) or MK-1248 and pembrolizumab (Arm 2; FAS2). These populations will be used for exploratory analyses of efficacy.

Analysis of response duration is based on all confirmed responders.

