## **8.6 Statistical Methods**

### **8.6.1 Statistical Methods for Efficacy Analyses**

This section describes the statistical methods that address the exploratory efficacy objectives.

For the subset of FAS1 subjects treated with the RP2D dose of MK-1248 and the subset of FAS2 subjects treated with the RP2D for combination of MK-1248 with pembrolizumab, the estimates of the ORR and DCR and the 95% confidence intervals for the estimates based on the Clopper-Pearson method [48] will be provided. For PFS, DOR, and time to confirmed response Kaplan-Meier plots will be provided. Graphic displays will be provided for the best target lesion response DOR.

The ORR, DCR, BOR, DOR, PFS, best target lesion response, and time to confirmed response in subjects treated with doses below the RP2 doses will be listed along with baseline characteristics.

For PFS, subjects without documented PD/death will be censored at the last disease assessment date or, if they started new anti-cancer treatment, at the last disease assessment before initiation of the new anticancer treatment.

Descriptive statistics will be provided for other exploratory efficacy parameters.

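### Duration of response ends only at documented progression, so a responder's death without it can enter the Kaplan-Meier plot only as censored, although the same death ends PFS

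*Combined protocol and SAP*

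**What the plan says.** Section 8.4.3 measures DOR from the first response that is later confirmed to "the date of first documented disease progression based upon irRECIST by the investigator review". Death is not named. PFS, in the same section, "is defined as the time from the start of treatment to progressive disease (PD) or death, whichever occurs earlier".

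Section 8.5.2 fixes the DOR population: "Analysis of response duration is based on all confirmed responders".

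Section 8.6.1 sets the display: "For PFS, DOR, and time to confirmed response Kaplan-Meier plots will be provided". It then gives one censoring rule, which begins "For PFS, subjects without documented PD/death will be censored at the last disease assessment date or, if they started new anti-cancer treatment" and, for subjects who switched treatment, goes back to the last assessment before the switch. There is no counterpart for DOR. Results "in subjects treated with doses below the RP2 doses will be listed along with baseline characteristics", so the plot concerns the RP2D subsets.

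Nothing elsewhere fills the gap. The irRECIST adaptations in Section 7.1.2.7.1 do not treat death as progression. Section 8.4.3 cites an Appendix 12.6 for irRECIST, but the table of contents lists appendices only up to 12.5.

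**The concern.** When progression is the only event, a responder who dies without documented progression cannot be an event. Section 8.5.2 does not allow that subject to be dropped. The remaining option in a Kaplan-Meier plot is a censored time, at a date the plan does not give. The same death is an event for PFS, so one subject's two time-to-event records disagree about whether the disease course has ended.

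Kaplan-Meier assumes that censoring carries no information about the event. That is hard to defend here. Section 5.1.2 enrols subjects with metastatic disease and no available therapy likely to help, and Section 7.1.2.6 spaces scans 9 weeks apart. A responder can deteriorate and die between scans. Censoring that death makes responses look more durable than they were.

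Little is at stake. DOR is exploratory and descriptive, the primary endpoint is DLT, and few responders are likely because "Enrollment into this study has been prematurely discontinued due to program prioritization".

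**Working it through.** The plan states no figure for DOR, so there is none to reproduce. The sizes below are illustrations.

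**Inputs.** From the plan: the event definitions and censoring rule above, and a planned RP2D cohort of 14 (Section 5.2.1.5: "The dose confirmation part will continue until 14 subjects are studied at the selected dose"). Assumed: constant hazards; a true median of 39 weeks to progression or death; a share *s* of responses ending in death without documented progression (5%, 10% or 20%); and an ORR of 10% to 30%.

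**Average effect.** If the hazard of progression or death is *h*, the hazard of progression alone is (1 − *s*)*h*. With deaths censored, the curve reads S(t)^(1 − *s*) and the median is multiplied by 1/(1 − *s*). The true value at 26 weeks is 0.5^(26/39) = 0.630.

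| *s* | 1/(1 − *s*) | 39-week median reads | S(26) reads |
|---|---|---|---|
| 5% | 1.05 | 41.1 | 0.630^0.95 = 0.645 |
| 10% | 1.11 | 43.3 | 0.630^0.90 = 0.660 |
| 20% | 1.25 | 48.8 | 0.630^0.80 = 0.691 |

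The multiplier does not depend on the 39-week assumption.

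**How often it would arise.** Expected responders: 14 × 0.10 = 1.4 to 14 × 0.30 = 4.2, so about 1 to 4, and fewer if the early stop left the cohort smaller. The chance that at least one of *n* responders is affected is 1 − (1 − *s*)^*n*:

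| *n* | *s* = 10% | *s* = 20% |
|---|---|---|
| 1 | 0.10 | 0.20 |
| 2 | 0.19 | 0.36 |
| 3 | 0.27 | 0.49 |
| 4 | 0.34 | 0.59 |

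**Against sampling error.** With 4 responders the standard error at 26 weeks is √(0.63 × 0.37 / 4) = 0.241, or 24 points. The average shifts are 0.645 − 0.630 = 1.5 points, 0.660 − 0.630 = 3.0 points and 0.691 − 0.630 = 6.1 points.

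**One data set.** Take four responses ending at weeks 18, 27, 36 and 45, one by death and three by progression. With the death counted, the curve steps through 0.75, 0.50, 0.25 and 0, and the median is 27 weeks (first time at or below 0.50).

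- Death first (week 18), censored: the curve stays at 1.00 past week 18, then 0.67, 0.33, 0. The median reads 36.
- Death second (week 27), censored: 0.75 at week 18, then 0.75 × 1/2 = 0.375 at week 36. The median reads 36.
- Death third or fourth, censored: 0.75 and 0.50 at weeks 18 and 27 as before. The median stays at 27.

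So the median moves in two of the four orderings. The 26-week value moves only when the death comes first (100% instead of 75%). Software that averages across the flat stretch at exactly 0.50 gives (27 + 36)/2 = 31.5 rather than 27 with the death counted. In the first two orderings the censored curve still reads longer, at 36.

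**The case against.** The strongest reply is that the upward shift is bias only if the target is time to progression or death. DOR as written targets time to progression. If deaths were independent of progression, censoring them would estimate that quantity correctly. PFS and DOR may legitimately have different end events, and the SAP never says in terms that deaths are censored. It is also loose to say that a censored responder is carried forward as still responding: the subject simply leaves the risk set.

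The size may be overstated as well. Section 7.1.2.7.1 records the initial progression date as the PD date once progression is confirmed, and it does not require a repeat scan in clinically unstable subjects. Section 7.1 allows unscheduled procedures. Each could lower *s*. One death in four responders is a share of 25%, above the range used for the averages. The documents do not show that an RP2D was established, so the plot may never be drawn. In listings, PFS appears beside DOR and would reveal the death.

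These points limit the size and the wording, and they stand as such. They do not rescue the definition. A progression-only target is never stated as a choice, independence is implausible in this population, and even that target needs a censoring rule and date, which are absent.

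**Conclusion.** The concern holds. Followed as written, the plan lets a responder's death without documented progression enter the DOR curve only as a censored time, at an unspecified date, while PFS counts it as an event. Relative to time to progression or death, the median is inflated by 1/(1 − *s*): 1.05- to 1.25-fold for *s* of 5% to 20%. This rests on constant hazards and an assumed *s*, for which the documents give no value.

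The practical consequence is low. With about 1 to 4 responders, sampling error exceeds the average shift several times over, lower-dose results are only listed, and no dose decision uses DOR. In a single small data set one early death can still visibly change the plot, and two analysts could draw different curves from the same data. The change is worth making because it is cheap.

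**What to change.** In Section 8.4.3, define DOR as the time from the first response that is later confirmed to the first documented irRECIST progression or death from any cause, whichever comes first. In Section 8.6.1, extend the PFS censoring rule to DOR: responders with neither event are censored at the last disease assessment or, if new anticancer treatment was started, at the last assessment before it. If the sponsor does want progression only, the SAP should say so and state how deaths and new treatment are handled and at what date.

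The cost is one or two sentences and no new data item. DOR may come out slightly shorter, and late deaths will be captured only as completely as they are for PFS. Under Section 7.2.3.1, deaths are reported as SAEs for 90 days after treatment stops, or 30 days if new therapy starts. In Arm 1 the fourth dose falls 3 × 21 = 63 days after the first, so the longer window closes at 63 + 90 = 153 days, or 21.9 weeks. That is about 12.9 weeks after a response first seen at week 9. Later deaths depend on the 9-weekly follow-up in Section 7.1.8.3.2 and on survival contacts that the sponsor may request under Section 7.1.8.4.

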#### 8.4.4 Derivations of Safety Endpoints

Description of safety measures is provided in Section 7.

### 8.5 Analysis Populations

#### 8.5.1 Safety Analysis Populations

The All-Subjects-as-Treated (ASaT) population will be used for the analysis of safety data in this study. The ASaT population consists of all subjects who received at least one dose of study treatment. In case of treatment administration errors, subjects will be analyzed according to the treatment they actually received. However, in the MK-1248 and pembrolizumab combination arm (i.e. Arm 2), if some subjects received only pembrolizumab, but did not receive any dose of MK-1248, these subjects will be included in the ASaT population, but their safety data will be presented separately. For DLT evaluation, ASaT subjects that were observed for safety for 21 days after the first dose of assigned treatment or experienced a DLT prior to 21 days after the first dose of assigned treatment (subjects evaluable for DLT as described in Section 5.2.4) will be used.

At least one laboratory or vital sign measurement obtained subsequent to at least one dose of study treatment is required for inclusion in the analysis of each specific parameter. To assess change from baseline, a baseline measurement is also required.

### **8.5.2 Efficacy Analysis Populations**

The full analysis set populations FAS1 and FAS2 are defined as all subjects with a baseline scan with measurable disease by investigator assessment who were administered MK-1248 (Arm 1; FAS1) or MK-1248 and pembrolizumab (Arm 2; FAS2). These populations will be used for exploratory analyses of efficacy.

Analysis of response duration is based on all confirmed responders.

## **8.6 Statistical Methods**

### **8.6.1 Statistical Methods for Efficacy Analyses**

This section describes the statistical methods that address the exploratory efficacy objectives.

For the subset of FAS1 subjects treated with the RP2D dose of MK-1248 and the subset of FAS2 subjects treated with the RP2D for combination of MK-1248 with pembrolizumab, the estimates of the ORR and DCR and the 95% confidence intervals for the estimates based on the Clopper-Pearson method [48] will be provided. For PFS, DOR, and time to confirmed response Kaplan-Meier plots will be provided. Graphic displays will be provided for the best target lesion response DOR.

The ORR, DCR, BOR, DOR, PFS, best target lesion response, and time to confirmed response in subjects treated with doses below the RP2 doses will be listed along with baseline characteristics.

For PFS, subjects without documented PD/death will be censored at the last disease assessment date or, if they started new anti-cancer treatment, at the last disease assessment before initiation of the new anticancer treatment.

Descriptive statistics will be provided for other exploratory efficacy parameters.

### **8.6.2 Statistical Methods for Safety Analyses**

Safety and tolerability will be assessed by clinical review of all relevant parameters including AEs, SAEs, laboratory tests, vital signs, ECG measurements and physical examinations.

DLTs will be listed. DLTs and adverse experiences will be summarized as counts and frequencies for each MK-1248 (Arm 1) or MK-1248 in combination with pembrolizumab dose level that had at least three subjects treated and listed for other dose levels. The estimate of the DLT rate among subjects treated with the RP2D and the 95% Bayesian probability interval for the estimate will be provided.

Laboratory assessments, vital signs, and other safety endpoints will be summarized as appropriate.

Immune-related AEs (irAEs) will be summarized in separate tables from other AEs. Any AE of unknown etiology associated with MK-1248 or MK-1248 in combination with pembrolizumab exposure will be evaluated to determine if it is possibly an AE of a potentially immunologic etiology).

In addition, the broad clinical and laboratory AE categories consisting of the percentage of subjects with any AE, a drug related AE, a serious AE, an AE which is both drug-related and

serious, and who discontinued due to an AE will be summarized for dose levels with at least 3 subjects treated and listed for other doses. Percentages of subjects in these categories among subjects treated with RP2D and 95% confidence intervals for the estimated percentages calculated using the Clopper-Pearson method [48] will be provided.

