##### **4.2.2.4.2 MK-1248 in Combination with Pembrolizumab**

As described previously, the combination of the anti-mouse GITR and anti-mouse PD-1 surrogate antibodies for MK-1248 and pembrolizumab showed greater efficacy in preclinical studies than either agent alone. Therefore, the combination of MK-1248 and pembrolizumab is planned for study in clinical trials to assess whether selected groups of patients with cancer may also derive greater benefit from the combination. As an initial step in testing the combination in clinical trials, this study will assess the safety and tolerability of the combination of MK-1248 and pembrolizumab, and determine a recommended Phase 2 dose for MK-1248 when used in combination with pembrolizumab. Similar to the preclinical studies, MK-1248 and pembrolizumab will be administered on the same day for the first 4 cycles in Arm 2 when both drugs are administered, followed by administration of pembrolizumab alone every 3 weeks for a total of 24 weeks or until a discontinuation criterion is met.

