##### **7.1.8.2 Treatment Period**

Visit requirements are outlined in Section 6.0 - Trial Flow Chart. Specific procedure-related details are provided above in Section 7.1 - Trial Procedures.

After a screening phase of up to 28 days, eligible subject will be assigned to one of 2 Arms and a dose level of MK-1248 by IVRS. In Arms 1 and 2, MK-1248 treatment will be administered on Day 1 of each 21-day cycle for up to a maximum of 4 cycles. In Arm 2, pembrolizumab will be administered on Day 1 of each 21 day cycle for up to 24 months of treatment.

Subjects will be followed until confirmed disease progression, unacceptable adverse event(s), intercurrent illness that prevents further administration of treatment, investigator's decision

to withdraw the subject, subject withdraws consent, pregnancy of the subject, noncompliance with study treatment or procedure requirements, or administrative reasons.

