All adverse events that occur after the consent form is signed but before randomization/treatment allocation must be reported by the investigator if they cause the subject to be excluded from the trial, or are the result of a protocol-specified intervention, including but not limited to washout or discontinuation of usual therapy, diet, placebo treatment or a procedure. From the time of randomization/treatment allocation through 30 days following cessation of treatment, all adverse events must be reported by the investigator. Such events will be recorded at each examination on the Adverse Event case report forms/worksheets. The reporting timeframe for adverse events meeting any serious criteria is described in section 7.2.3.1. The investigator will make every attempt to follow all subjects with non-serious adverse events for outcome.

Electronic reporting procedures can be found in the EDC data entry guidelines. Paper reporting procedures can be found in the Investigator Trial File Binder (or equivalent).

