### 7.2.3 Immediate Reporting of Adverse Events to the Sponsor

#### 7.2.3.1 Serious Adverse Events

A serious adverse event is any adverse event occurring at any dose or during any use of Sponsor's product that:

- Results in death;
- Is life threatening;
- Results in persistent or significant disability/incapacity;
- Results in or prolongs an existing inpatient hospitalization;
- Is a congenital anomaly/birth defect;
- Is an other important medical event.

**Note:** In addition to the above criteria, adverse events meeting either of the below criteria, although not serious per ICH definition, are reportable to the Sponsor in the same timeframe as SAEs to meet certain local requirements. Therefore, these events are considered serious by the Sponsor for collection purposes.

- Is a new cancer (that is not a condition of the study);
- Is associated with an overdose.

Refer to [Table 9](#) for additional details regarding each of the above criteria.

Progression of the cancer under study is not considered an adverse event unless it results in hospitalization or death.

For the time period beginning when the consent form is signed until randomization/treatment allocation, any serious adverse event, or follow up to a serious adverse event, including death due to any cause, that occurs to any subject must be reported within 24 hours to the Sponsor if it causes the subject to be excluded from the trial, or is the result of a protocol-specified intervention, including but not limited to washout or discontinuation of usual therapy, diet, placebo treatment or a procedure.

For the time period beginning at randomization/treatment allocation through 90 days following cessation of treatment, or 30 days following cessation of treatment if the subject initiates new anticancer therapy, whichever is earlier, any serious adverse event, or follow up to a serious adverse event, including death due to any cause, whether or not related to the Sponsor's product, must be reported within 24 hours to the Sponsor either by electronic media or paper. Electronic reporting procedures can be found in the EDC data entry guidelines. Paper reporting procedures can be found in the Investigator Trial File Binder (or equivalent).

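### Section 8.6.2 sets no time window or phase split for Arm 2 adverse events, so events from the pembrolizumab-alone phase are counted under MK-1248 dose levels

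*Combined protocol and SAP*

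**What the plan says.** Section 8.6.2 states that "adverse experiences will be summarized as counts and frequencies for each MK-1248 (Arm 1) or MK-1248 in combination with pembrolizumab dose level" with at least three subjects treated; smaller dose levels are listed. It adds Clopper-Pearson 95% intervals at the RP2D for five categories: any AE, drug-related AE, serious AE, drug-related serious AE, and discontinuation due to an AE. It names no time window, treatment phase or exposure denominator.

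Treatment length (Section 7.1.8.2): "MK-1248 treatment will be administered on Day 1 of each 21-day cycle for up to a maximum of 4 cycles", whereas "pembrolizumab will be administered on Day 1 of each 21 day cycle for up to 24 months of treatment". The trial summary (Section 1.0) also gives 24 months. Section 4.2.2.4.2 instead describes the four joint cycles as "followed by administration of pembrolizumab alone every 3 weeks for a total of 24 weeks or until a discontinuation criterion is met".

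Collection (Section 7.2): "From the time of randomization/treatment allocation through 30 days following cessation of treatment, all adverse events must be reported by the investigator". Serious events (Section 7.2.3.1) run "through 90 days following cessation of treatment, or 30 days following cessation of treatment if the subject initiates new anticancer therapy, whichever is earlier", and Section 7.2.3.2 sets the same limits for events of clinical interest (ECIs). None of these limits is tied to the last MK-1248 dose.

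Section 8.2 allows lock once all subjects not lost to progression, death or withdrawal of consent are at least 6 months past first dose. Arm 2 escalates from 0.12 mg through Table 3.

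**The concern.** Primary objective 2 is the safety and tolerability of MK-1248 given with pembrolizumab, and the by-dose tables are where a reader will look for it. As the rules stand, a row labelled with an MK-1248 dose combines events from the joint phase with events that start long after MK-1248 has stopped. A subject who stops pembrolizumab for an AE in month 15 would count in the discontinuation row of an MK-1248 dose last given about a year earlier.

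Follow-up may also differ by dose. Low-dose cohorts enrol first, so at a lock near the minimum they will have had more time in which to report an event. That can make low doses look worse, or a rising trend look flatter, with no true dose effect. The two arms are also tabulated over very different lengths of time.

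**Working it through.** **The plan's own figures (Section 8.9.1, Scenario 1).** Arm 1: 8 + 9×3 + 11 = 46. Arm 2: 13×3 + 11 = 50. Total 96. Enrolment: 16 + 38 + 50 = 104 weeks. Duration: 104 weeks + 2 years ≈ 4.0 years. All agree with the plan.

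**Collection windows from first dose, on the 24-month text.** The fourth MK-1248 dose falls 3×21 = 63 days after the first.

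- Arm 1: AEs to 63 + 30 = 93 days; SAEs and ECIs to 63 + 90 = 153 days.
- Arm 2 completer: 24 months is 730.5 days, which holds 35 three-weekly doses. AEs run to 34×21 + 30 = 744 days, 8 times Arm 1's window. Of the 35 cycles, 31 (89%) are without MK-1248.

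**Length of the pembrolizumab-alone phase.**

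- 24 months: 730.5 − 84 = 646.5 days, or 21.2 months (92.4 weeks).
- 24 weeks read as the total: 24 − 12 = 12 weeks, half the course.

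**Difference by enrolment order.** The earliest lock under Scenario 1 is week 104 + 26 = 130. The first Arm 2 cohort starts at about week 12 to 16 and so can have completed 24 months, with 92 weeks on pembrolizumab alone. A subject enrolled at week 104 has 26 − 12 = 14 weeks. The ratio is 6.6 if nobody discontinues.

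The documents give no time on treatment, so I assume it is exponential with median M months. The rate per week is λ = ln 2/(4.348 M), and expected pembrolizumab-alone weeks are (e^(−12λ) − e^(−Lλ))/λ, with L = 104.4 (first cohort) or 26 (last). For M = 4, λ = 0.0399: (0.620 − 0.016)/0.0399 = 15.2 against (0.620 − 0.355)/0.0399 = 6.7.

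**Effect on a percentage.** I assume the same first-event risk h per cycle at every dose and in every cycle. The last subject has 9 cycles (26 weeks) and the first cohort up to 35.

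- No discontinuation: 1 − (1 − h)^k gives 8.6% against 29.7% at h = 1% and 16.6% against 50.7% at h = 2%. The excess is 21 and 34 points.
- With discontinuation: let r = 0.5^(21/(30.44 M)) be the chance of staying on from one cycle to the next, and q = (1 − h)r. The excess is h(q^9 − q^35)/(1 − q). For M = 12 and h = 1%: r = 0.961, q = 0.951, and 0.01×(0.638 − 0.174)/0.0487 = 9.5 points.

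| Assumed median on treatment | Pembrolizumab-alone weeks, first vs last | Ratio | Low-dose excess, h = 1% to 2% |
|---|---|---|---|
| 2 months | 4.8 vs 3.2 | 1.5 | 0.5 to 0.8 points |
| 4 months | 15.2 vs 6.7 | 2.3 | 2.5 to 4.2 points |
| 6 months | 25.0 vs 8.5 | 2.9 | 4.7 to 7.9 points |
| 12 months | 45.4 vs 10.9 | 4.2 | 9.5 to 15.8 points |
| No discontinuation | 92 vs 14 | 6.6 | 21 to 34 points |

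If the lock waits until every subject could have completed 24 months, the ratio is 1 and the excess is nil. The same holds at the 6-month minimum if pembrolizumab totals 24 weeks, because every course would then have ended.

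**The case against.** The strongest reply is that Section 8.6.2 is silent on the window and does not itself prescribe whole-period counting. That is correct: the reading is inferred from the missing window together with the collection rules. But nothing else in the plan supplies a cut-off.

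Second, the plan has partial safeguards. Section 8.5.1 presents pembrolizumab-only data separately, Section 7.2.4 allows attribution to one agent, irAEs get their own tables, and Section 8.12 summarises doses of each drug. None of these closes the gap. The Section 8.5.1 rule covers only subjects who never received MK-1248. Attribution defaults to the combination, and three of the five RP2D categories (any AE, serious AE, discontinuation due to an AE) ignore causality. The irAE tables have no window either, and exposure is a count of doses that no AE rate uses as a denominator.

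Third, the size is easily overstated, and this objection largely stands. A reader might infer that a 21 to 34 point distortion is to be expected, enough to hide or reverse a dose trend. That requires every subject to stay on treatment for 24 months, in a population with metastatic disease and no available therapy likely to help. With 3 to 6 subjects per escalation dose level (0 of 3 has an upper 95% limit of 71%), the smaller excesses could not be told apart from chance. The lock rule is also a minimum: Section 8.9.1 runs the study to the end of the last Part E subject's 2-year treatment. Because enrolment closed early and the documents give neither numbers nor start date, the gradient cannot be sized for the trial as run.

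Fourth, a reader might infer that late events are wrongly charged to MK-1248. The rows are labelled as the combination, and Section 5.2.3.1 says events may appear several months after the last dose, so some may be due to MK-1248. Nor is any formal comparison of the arms planned, so the unequal windows affect reading across tables rather than a test.

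**Conclusion.** The concern holds as a gap in the tabulation rule. Following the plan as written, Arm 2 AE counts and the RP2D percentages mix joint-phase and pembrolizumab-alone events under MK-1248 dose levels. The pembrolizumab-alone phase is up to about 21 months on the 24-month text and about 12 weeks if 24 weeks is the total. Sections 1.0 and 7.1.8.2 must be reconciled with Section 4.2.2.4.2 before either figure is relied on.

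The dose gradient is conditional. It needs a lock near the 6-month minimum and the longer pembrolizumab course. On the assumed 1–2% per-cycle risk and 2- to 12-month medians, the apparent low-dose excess runs from 0.5–0.8 to 9.5–15.8 points; 21–34 points is an upper bound.

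The documents do not support extending this to the primary endpoint. DLTs are confined to Cycle 1, so DLT-based escalation and the RP2D DLT rate are unaffected. This is a cheap improvement to the safety tables, not a flaw in dose finding.

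**What to change.** In Section 8.6.2, for Arm 2, present the AE summaries and the RP2D percentages with intervals for two periods, assigned by onset date:

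1. First dose through 30 days after the last MK-1248 dose for AEs, and through 90 days for SAEs and ECIs (30 days if new anticancer therapy starts earlier). These match the Arm 1 collection limits. A single 30-day cut for everything would drop Arm 2 serious events that Arm 1 keeps.
2. The whole treatment period with its follow-up, as now.

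Separately, reconcile the two stated pembrolizumab durations.

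The cost is SAP wording and one extra set of tables. No new data are needed, because Table 9 already requires AE start dates. The drawback is that delayed events possibly due to MK-1248, with onset after the first window, appear only in the second set. Both sets should therefore be kept and read together.
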